1.3. Overall Rationale for the Study

The proposed clinical study in healthy HIV-uninfected subjects will evaluate the safety/tolerability and the immunogenicity of 2 different prime/boost regimens: priming with Ad26.Mos4.HIV and boosting with Ad26.Mos4.HIV and either Clade C gp140 plus adjuvant or a combination of Clade C and Mosaic gp140 plus adjuvant. The goal of this study is to evaluate if the addition of Mosaic gp140 to Clade C gp140 improves the breadth of humoral immune responses (defined as immune recognition of diverse strains/clades of HIV), which will ultimately assist in the selection of the best regimen(s) for evaluation in future efficacy studies.

To assess the durability of the immune responses, a Long-term Extension (LTE) phase of approximately 3 years was introduced for subjects randomized to Group 1 or Group 2, who have received all 4 vaccinations and are negative for HIV infection at the end of the main study. The vaccination regimens of Group 1 and Group 2 (including Ad26.Mos4.HIV and either Clade C gp140 alone or combined with Mosaic gp140) form the basis for the regimens that will likely be evaluated in future studies.

In addition, subjects enrolled in the LTE phase will be offered participation in an extension of the LTE phase. Eligible subjects who consent to participation will be randomized (3:1 ratio) to receive a boost vaccination with Ad26.Mos4.HIV together with bivalent gp140 or placebo at Week 192 (-4 weeks/+4 months [Visit 22a], ie, approximately 3 years after the 4th vaccination of the primary vaccination series). The goal is to evaluate the impact of a late boost vaccination on the quantity (including magnitude and breadth) and quality of the immune response (humoral and cellular) as well as the safety of such late boost vaccination.

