#### Humoral response

For all the humoral assays the immune response values will be  $\log_{10}$ -transformed before any further handling. The  $\log_{10}$ -transformed values will be used throughout the analysis. In the graphs, original values will be displayed on the  $\log_{10}$  scale.

For each assay and at each time point geometric mean of actual values, geometric mean increases and percentage of responders, all with corresponding 95% CIs will be provided by group in the tables. Within each group, the mean fold change of Week 52 to Week 72 will be reported. The definition of responders is defined in section 6.4. for each assay. Graphical presentations will be provided displaying dots for the subject values and including the geometric mean and the percentage of responders. If available, baseline values will be summarized pooling all the groups and will be displayed on the left of each graph. Data from post-baseline timepoints will be plotted next to each other for each group, a symbol will identify the geometric mean (or the median) of each group and timepoint.

In the graphs the actual values will be shown and the LLOQ cut-off will be visualized, the values below LLOQ or below LOD will be visualized with the value imputed as described in section 6.3.

Graphs by subgroups listed in section 2.4 will be done for ELISA (Clade C C97ZA.012, Mos1) and for ADCP (Clade C C97ZA.012), Mos1).

Durability will be displayed as a line plot showing the GM/median for each vaccine regimen.

Magnitude-breadth (MB) plot for the ELISA assay will be provided at post-baseline timepoints to explore the magnitude and breadth of each individual serum sample assayed (antibody titers of 5 Clades). MB curves will show, for each possible titer threshold, the proportion of antibody titers greater than this threshold. The group-specific curve obtained as the average MB across all subjects in that group will be displayed. The AUC-MB is calculated as the average of the titers over the panel of antigens.

For BAMA the median will be reported instead of the geometric mean. Cumulative number of responses across the IgG/antigen classes will be tabulated.

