**6.4. Handling of Missing and/or Invalid Immune Response Data**

Analysis will be carried out on the available data, no imputation will be done for missing samples. BAMA and ICS unreliable values should be excluded from the analysis: those records will be flagged in the SDTM dataset.

LLOQs by assay/test are listed in section 6.5. Values below LLOQ or LOD will be handled as follows:

- Calculation of Geomean (humoral response except ADCP) and median (cellular response):
  - o values < LLOQ are imputed =LLOQ/2
  - o values = LOD are imputed =LLOQ/2

For ADCP only:

- o values < LOD are imputed =LOD/2

- Calculation of fold increases from baseline:
  - o values <LLOQ are imputed =LLOQ
  - o values =LLOQ are imputed = LLOQ

For ADCP only:

- o values < LOD are imputed =LOD

Values above the upper limit of quantification (ULOQ) will be handled as follows:

- Calculation of geomean and median:
  - o Values>ULOQ are imputed=ULOQ.
- Calculation of fold increases from baseline:
  - o Values >ULOQ are imputed with ULOQ

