**6.5. Immune response assays: details**

The details for each immune response assay are listed in following table. The final framework will be reported in the DPS, as not all details might be available at the time this SAP has to be approved.

Assay	Test	Lab	LLOQ a	LOD a	ULOQ a	Unit	Responder definition/Positivity (if baseline is not available)
ELISA	Ad26 VNA	Janssen Vaccines and Prevention	17	NA	NA	IC90	>LLOQ
Env ELISA IgG-t gp140	Clade A (92UG037.1) Clade B (1990a) Clade C (Con C) Clade C (C97ZA.012) Mos1	Janssen Vaccines and Prevention	625 156.25 625 156.25 78.125	0	1600000 800000 1600000 1250000 1250000	EU/ml	1) if baseline <LLOQ or missing, R>LLOQ 2) if baseline >=LLOQ, R=3-fold increase from baseline
Env ELISA IgG1-3	Clade C (C97ZA.012) IgG1 Clade C (C97ZA.012) IgG3	BIDMC	12.3 12.4	4	403.4 120.8	EC50	
Env ADCP gp140	Clade A (92UG037.1) Clade B (1990a) Clade C (Con C) Clade C (C97ZA.012) Mos1	Ragon	NA	5.16 6.43 6.49 4.32 4.28	NA	PS	1) if baseline <LOD or missing, R>LOD 2) if baseline >=LOD, R=3-fold increase from baseline
VNA	TZM-bl Clade B (6535.3) TZM-bl Clade B (BZ167.12) TZM-bl Clade B (Bx08.16) TZM-bl Clade B (SF162.LS) TZM-bl Clade B (SS1196.1)	Seaman (BIDMC)	20	NA	43740	ID50	>LLOQ
TZM-bl b	Clade C (MW965.26) Clade C (97ZA012.12) b Clade C (ZM233M) Clade C (CE703010010) Clade C (2759058)	Duke U	10	NA	21870	ID50	>LLOQ

a In case final LLOQ and ULOQ values present in the dataset differ from those listed in this table, those provided from the lab should be used.

b At Week 52 samples that have a titer >500 against MW965.26 or >50 against 97ZA012.12 at Week 28 will be assayed against ZM233M, CE703010010, 2759058, ZM215F, SO431, CE704810053.  
Samples that have a titer >50 against MW965.26 at visit 15 (Wk52) will be assayed against MW965.26 at visit 17 (Wk72). Samples that have a titer >10 against 97ZA012.12 at visit 15 (Wk52) will be assayed against 97ZA012.12 at visit 17 (Wk 72).

Assay	Test	Lab	LLOQ a	LOD a	ULOQ a	Unit	Responder definition/Positivity (if baseline is not available)
	Clade C (ZM215F) Clade C (SO431) Clade C (CE704810053)						

BAMA IgG3	HIV ENV Con S gp140 CFI (Clade M) HIV ENV Con 6 gp120/B (Clade M) HIV ENV gp41 HIV ENV 1086C_D7gp120 (Clade C) HIV ENV 1086C gp140 (Clade C) HIV ENV 1086C_V1V2 (Clade C) HIV ENV gp70_B.Case A_V1V2 (Clade B)	Duke U	100 e	NA	NA	MFI	BAMA interpretation= 1

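### The ELISA magnitude-breadth curve shows 40% breadth between 78 and 312 EU/ml for a serum that is below the LLOQ on all five antigens

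*SAP*

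**What the plan says.** Protocol 1.3 sets the study goal as learning whether adding Mosaic gp140 "improves the breadth of humoral immune responses (defined as immune recognition of diverse strains/clades of HIV"). Protocol 2.1 makes the titres and breadth of Env-binding antibody a primary endpoint. Protocol 11.4 counts binding breadth as the number of clades to which a subject responds, and compares the areas under the magnitude-breadth (MB) curves between groups by a Wilcoxon-Mann-Whitney test.

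SAP 6.3 (Humoral response) plans the ELISA MB plot "to explore the magnitude and breadth of each individual serum sample assayed (antibody titers of 5 Clades"). It defines the curve: "MB curves will show, for each possible titer threshold, the proportion of antibody titers greater than this threshold". It also defines the summary: "The AUC-MB is calculated as the average of the titers over the panel of antigens". On graphs in general it says that "the values below LLOQ or below LOD will be visualized with the value imputed as described in section 6.3". The rule is in fact in SAP 6.4: "values < LLOQ are imputed =LLOQ/2".

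SAP 6.5 lists the antigens as "Clade A (92UG037.1) Clade B (1990a) Clade C (Con C) Clade C (C97ZA.012) Mos1", with LLOQs in the same order of "625 156.25 625 156.25 78.125" EU/ml. Its responder rule judges each antigen against its own LLOQ or its own baseline. The SAP gives no censoring rule, lower axis limit or LLOQ scaling specific to the MB curve.

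**The concern.** A common threshold is fair only if a non-response sits at the same place for every antigen. Here it does not. An unquantifiable Clade A or Con C result is placed at 312.5 EU/ml, above a genuine Mos1 titre of 300, which is 300/78.125 = 3.8 times the Mos1 LLOQ. The curve therefore counts some non-responses as recognition and ranks them above real responses to other antigens.

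The MB plot is the only ELISA breadth summary in the SAP. The clade count of protocol 11.4 is not carried into SAP 6.3 for ELISA, and a cumulative count of responses is planned only for BAMA. A reader judging breadth from the ELISA plot would see recognition that the SAP's own responder rule denies.

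**Working it through.** **Inputs.** LLOQs are from SAP 6.5, the half-LLOQ rule is from SAP 6.4, and the curve definition (share of titres strictly above t) is from SAP 6.3. The documents state no breadth value for a negative serum, so there is no figure of theirs to reproduce.

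| Antigen | LLOQ (EU/ml) | LLOQ/2 | log10(LLOQ/2) |
|---|---|---|---|
| Clade A 92UG037.1 | 625 | 312.5 | 2.495 |
| Clade B 1990a | 156.25 | 78.125 | 1.893 |
| Clade C Con C | 625 | 312.5 | 2.495 |
| Clade C C97ZA.012 | 156.25 | 78.125 | 1.893 |
| Mos1 | 78.125 | 39.0625 | 1.592 |

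Spread of LLOQs: 625/78.125 = 8.

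**Curve for a serum below the LLOQ on all five.** MB(t) = (number of imputed titres > t)/5.

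- t < 39.0625: 5/5 = 100%
- 39.0625 ≤ t < 78.125: 4/5 = 80%
- 78.125 ≤ t < 312.5: 2/5 = 40%
- t ≥ 312.5: 0%

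The first two steps lie below every LLOQ. At thresholds where at least one antigen is quantifiable, false breadth is at most 40%. It comes from Clade A and Con C, neither of which can be quantified in that band.

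**AUC-MB of the same serum.** (2.495 + 1.893 + 2.495 + 1.893 + 1.592)/5 = 2.07 log10, a geometric mean of about 118 EU/ml. That is above the Mos1 LLOQ.

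**One real response.** With Mos1 at 300 and the other four below the LLOQ, the curve shows 3/5 = 60% from 78.125 to below 300, then 40% up to 312.5. Counting responses only, it should show 1/5 = 20%, then 0%.

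**Alternative imputation.** SAP 6.4 uses the LLOQ itself for fold increases. Applied to the curve, this gives an all-negative serum 80% from 78.125 to below 156.25, 40% from 156.25 to below 625, and 0% from 625. That is worse.

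**Is the second Clade C antigen the cause?** No. Dropping Con C leaves 75%, then 25%; dropping C97ZA.012 leaves 75%, then 50%. The cause is the unequal floors.

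**With the antigen-specific gate.** The all-negative serum scores 0% at every threshold. The Mos1-only serum scores 20% below 300 and 0% from there.

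**The case against.** **The rule is inferred.** SAP 6.4 lists LLOQ/2 for geometric means and medians. The sentence carrying imputed values into graphs sits with the dot plots, before the MB plots are introduced, and points to the wrong section. SAP 6.5 treats the LLOQs as provisional and leaves the final assay framework to a later document. This stands as a caveat. But the only other imputation in the SAP does worse, and updated LLOQs would not help unless they happened to be equal.

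**Below the LLOQ is not zero.** A Clade A value below 625 might truly be 400. That is correct, but it is no reason to draw the value as exceeding every threshold up to 312.5. Protocol 11.4 and SAP 6.5 both treat it as no response.

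**Little hangs on it.** No formal hypothesis is tested. SAP 6.3 also gives responder percentages by assay, separate geometric mean ratios between the active groups for Clade C, Mos1 and Clade B, and BAMA MB curves over a larger panel. The ULOQs are 800,000 to 1,600,000 EU/ml, so the affected band (a factor of 4, or 0.6 log10) is the bottom of an axis of about four decades. All of this stands and limits the consequence.

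**Stronger readings that the documents do not support:**

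- *The artefact favours a regimen.* The floors are identical in every group.
- *Long-term samples are the worst affected.* No titre distribution is given for them, and protocol 1.1.2.2 reports binding responses maintained to Week 120 in the related study.
- *Clade C must be down-weighted.* Protocol 1.3 speaks of strains as well as clades, and SAP 6.3 averages over antigens, so equal weight per antigen is a legitimate choice.
- *The curve should start at 625 EU/ml.* That would discard quantifiable titres for Mos1 (78 to 625) and for Clade B and C97ZA.012 (156 to 625).

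**Conclusion.** The point holds in a limited form. As written, the ELISA MB curve gives a fully unquantifiable serum 40% breadth from 78.125 to below 312.5 EU/ml and 0% from 312.5. A reader might quote 80%, but that step lies wholly below every LLOQ and should not be used as the size of the problem.

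The result assumes that SAP 6.4's LLOQ/2 rule governs the MB plot and that the tabulated LLOQs stay as they are. If every sample in a placebo group were below the LLOQ on all five antigens, that group's mean curve would show the same 40% plateau. Where all titres exceed their LLOQs the effect is nil, so post-dose peak comparisons of the active groups should be little affected. How many vaccinated subjects' samples fall low enough to matter cannot be told from the documents.

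Separately, the label is wrong: five antigens cover three clades, with C entered twice, plus a mosaic. That is a clerical matter.

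**What to change.** In SAP 6.3, for the ELISA MB curve:

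1. Count an antigen at threshold t only if its titre is at or above that antigen's own LLOQ (or the sample meets the SAP 6.5 responder rule for it) and exceeds t. Choose one gate and name it.
2. Start the threshold axis at the lowest LLOQ in the panel, 78.125 EU/ml on the present table.
3. State that AUC-MB is the mean log10 titre with LLOQ/2 for below-LLOQ values. Note that it is then not the exact area under the gated curve, and that an all-negative serum has a value of 2.07.
4. Point the graph sentence to SAP 6.4, and relabel the panel as 5 antigens (Clades A, B, C twice, and Mos1).

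Leave the antigen weights as they are. The cost is a few lines of SAP text and the reprogramming of one derived variable and one plot. The downside is less direct comparability with earlier MB plots. SAP 1 says that outputs up to Week 72 will not be repeated, so any earlier curve shown beside a new one needs a rerun or a note on the change of rule.

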### **Cellular response**

For ELISpot and for each peptide: n, median, quartile range, min, max of actual values, percentage of responders above a predefined threshold (see section 6.4) and corresponding 95% CI will be tabulated.

Graphical presentations will be provided displaying dots for the subject values and including the median and the percentage of responders. In the graphs the actual values will be shown and the LLOQ cut-off will be visualized, the values below LLOQ will be visualized with the value imputed as LLOQ/2.

In the graphs, original values will be displayed on the  $\log_{10}$  scale. Graphs by subgroups listed in section 2.4 will be done for ELISpot Env peptide pool PTE, Gag peptide pool PTE and Pol peptide pool PTE.

### ICS

*T cells: CD4+, CD8+*

*Antigen: Combined pools and separated pools*

Cytokine counts: Marginal, Boolean AND (co-expression) counts, Boolean OR (and/or)

For CD4+ and CD8+ and for each antigen (combined and separated pools): n, median, quartile range, min, max, percentage of responders (see section 6.4) and corresponding 95% CI will be tabulated for each available cytokine background adjusted percentages listed below.

Cytokine (ISSCAT)	Description
CD154+	Marginal
GzB+	Marginal
ICOS+	Marginal
IFNg+	Marginal
IL2+	Marginal

IL17a+	Marginal
IL4+	Marginal
TNFa+	Marginal
IFNg+/IL2+	Boolean AND (co-expression)
IFNg+/IL2+/TNFa+	Boolean AND (co-expression)
IFNg+/TNFa+	Boolean AND (co-expression)
IL2+/TNFa+	Boolean AND (co-expression)
IFNg+ or IL2+	Boolean OR (and/or)
IFNg+ or IL2+ or TNFa+	Boolean OR (and/or)

Graphical presentations will be provided displaying dots for the subject values and including the median and the percentage of responders. In the graphs, original values will be displayed on the log10 scale.

The technical details for the calculation of the cytokine background adjusted percentages to be displayed in the above described outputs will be outlined in the DPS.

Additional timepoints and tests within one of the above listed assays may be investigated for exploratory purposes. Those data will be analyzed using the approaches described in this SAP.

**6.4. Handling of Missing and/or Invalid Immune Response Data**

Analysis will be carried out on the available data, no imputation will be done for missing samples. BAMA and ICS unreliable values should be excluded from the analysis: those records will be flagged in the SDTM dataset.

LLOQs by assay/test are listed in section 6.5. Values below LLOQ or LOD will be handled as follows:

- Calculation of Geomean (humoral response except ADCP) and median (cellular response):
  - o values < LLOQ are imputed =LLOQ/2
  - o values = LOD are imputed =LLOQ/2

For ADCP only:

- o values < LOD are imputed =LOD/2

- Calculation of fold increases from baseline:
  - o values <LLOQ are imputed =LLOQ
  - o values =LLOQ are imputed = LLOQ

For ADCP only:

- o values < LOD are imputed =LOD

Values above the upper limit of quantification (ULOQ) will be handled as follows:

- Calculation of geomean and median:
  - o Values>ULOQ are imputed=ULOQ.
- Calculation of fold increases from baseline:
  - o Values >ULOQ are imputed with ULOQ

**6.5. Immune response assays: details**

The details for each immune response assay are listed in following table. The final framework will be reported in the DPS, as not all details might be available at the time this SAP has to be approved.

Assay	Test	Lab	LLOQ a	LOD a	ULOQ a	Unit	Responder definition/Positivity (if baseline is not available)
ELISA	Ad26 VNA	Janssen Vaccines and Prevention	17	NA	NA	IC90	>LLOQ
Env ELISA IgG-t gp140	Clade A (92UG037.1) Clade B (1990a) Clade C (Con C) Clade C (C97ZA.012) Mos1	Janssen Vaccines and Prevention	625 156.25 625 156.25 78.125	0	1600000 800000 1600000 1250000 1250000	EU/ml	1) if baseline <LLOQ or missing, R>LLOQ 2) if baseline >=LLOQ, R=3-fold increase from baseline
Env ELISA IgG1-3	Clade C (C97ZA.012) IgG1 Clade C (C97ZA.012) IgG3	BIDMC	12.3 12.4	4	403.4 120.8	EC50	
Env ADCP gp140	Clade A (92UG037.1) Clade B (1990a) Clade C (Con C) Clade C (C97ZA.012) Mos1	Ragon	NA	5.16 6.43 6.49 4.32 4.28	NA	PS	1) if baseline <LOD or missing, R>LOD 2) if baseline >=LOD, R=3-fold increase from baseline
VNA	TZM-bl Clade B (6535.3) TZM-bl Clade B (BZ167.12) TZM-bl Clade B (Bx08.16) TZM-bl Clade B (SF162.LS) TZM-bl Clade B (SS1196.1)	Seaman (BIDMC)	20	NA	43740	ID50	>LLOQ
TZM-bl b	Clade C (MW965.26) Clade C (97ZA012.12) b Clade C (ZM233M) Clade C (CE703010010) Clade C (2759058)	Duke U	10	NA	21870	ID50	>LLOQ

a In case final LLOQ and ULOQ values present in the dataset differ from those listed in this table, those provided from the lab should be used.

b At Week 52 samples that have a titer >500 against MW965.26 or >50 against 97ZA012.12 at Week 28 will be assayed against ZM233M, CE703010010, 2759058, ZM215F, SO431, CE704810053.  
Samples that have a titer >50 against MW965.26 at visit 15 (Wk52) will be assayed against MW965.26 at visit 17 (Wk72). Samples that have a titer >10 against 97ZA012.12 at visit 15 (Wk52) will be assayed against 97ZA012.12 at visit 17 (Wk 72).

Assay	Test	Lab	LLOQ a	LOD a	ULOQ a	Unit	Responder definition/Positivity (if baseline is not available)
	Clade C (ZM215F) Clade C (SO431) Clade C (CE704810053)						

BAMA IgG3	HIV ENV Con S gp140 CFI (Clade M) HIV ENV Con 6 gp120/B (Clade M) HIV ENV gp41 HIV ENV 1086C_D7gp120 (Clade C) HIV ENV 1086C gp140 (Clade C) HIV ENV 1086C_V1V2 (Clade C) HIV ENV gp70_B.Case A_V1V2 (Clade B)	Duke U	100 e	NA	NA	MFI	BAMA interpretation= 1
BAMA Breadth	HIV ENV gp120 Clade A (51802) IgG-t Ab Clade AE (254008) IgG-t Ab Clade AE (A244) IgG-t Ab Clade B (B.6240) IgG-t Ab Clade B (BORI) IgG-t Ab Clade B (TT31P) IgG-t Ab Clade BC (CNE20) IgG-t Ab Clade BC(BJOX002) IgG-t Ab Clade C(1086C_D7) IgG-t Ab B Clade M (Con 6) IgG-t Ab +12 more (will be listed in DPS) HIV ENV gp140 Clade B (SC42261) IgG-t Ab Clade C (CH505TF) IgG-t Ab C Clade A (9004S) IgG-t Ab						

e This is not LLOQ but “positive” threshold as provided by the lab

	C Clade B (RHPA) IgG-t Ab C Clade B (WITO)IgG-t Ab C Clade C (1086C) IgG-t Ab C Clade C (BF1266) IgG-t Ab CF Clade AE (conAE) IgG-t Ab CFI Clade M(Con S) IgG-t Ab  HIV ENV gp41 IgG-t Ab  HIV ENV gp70 Clade A (191084)IgG-t Ab Clade AE (C2101) IgG-t Ab Clade AE (CM244) IgG-t Ab Clade B (62357.14) IgG-t Ab Clade B (CaseA) IgG-t Ab Clade B (RHPA4259) IgG-t Ab Clade B (TT31P) IgG-t Ab Clade B(700010058) IgG-t Ab Clade BC (BJOX) IgG-t Ab Clade C (96ZM651) IgG-t Ab Clade C (BF1266) IgG-t Ab Clade C (CAP210) IgG-t Ab Clade C(Ce1086) IgG-t Ab Clade C(TV1.21)IgG-t Ab Clade C (001428)IgG-t Ab Clade C (7060101641)IgG-t Ab							
ELISpot	Env peptide pool Mos1 Pol peptide pool Mos1 Gag peptide pool Mos1 Env peptide pool Mos2 Pol peptide pool Mos2 Gag peptide pool Mos2	BIDMC	55	0	NA	SFC/10  PBMC	1) if baseline <threshold or missing, R>threshold 2) if baseline >=threshold, R=3-fold increase from baseline	73 g 112 87 70 63 55 100

g Threshold for ELISpot test is based on the 95 percentile from the baseline values of about 350 subjects on that test in the HIV-V-A004 study

	Env peptide pool PTE f (Env peptide pool 1 PTE, Env peptide pool 2 PTE, Env peptide pool 3 PTE) Pol peptide pool PTE Gag peptide pool PTE							105 181
ICS (CD4+, CD8+)	Combined pools HIV Gag pep pool HIV Pol pep pool (Mos1) HIV ENV pep pool (Mos1 ZA) HIV Env Pol Gag pep pool  Separated pools HIV Pol RT pep pool (Mos1) HIV Gag pep pool (Mos1) HIV Pol RNaseInt pep pool 1 (Mos1) HIV ENV gp120 pep pool 1 (Mos1) HIV ENV gp41 pep pool 1 (Mos1) HIV ENV gp120 pep pool clade C (ZA) HIV ENV gp41 pep pool clade C (ZA) HIV ENV pep pool 1 (Mos2)	FHCRC	NA	NA	NA	% of CD4+/C D8+ T cells	ICS interpretation=1 for cytokine combination: IFN+ or IL2+. Otherwise Fisher exact test comparing for each antigen the total cytokine count of the considered antigen with the sum of total cytokine counts in the negative controls.	

NA: not applicable; PS: phagocytic score; SFC: spot forming cells, PBMC: peripheral blood mononuclear cell, MFI: median fluorescent intensities

f ENV pep pool (PTE) will be provided split in pool 1,2,3: for the purpose of the statistical analysis they will be reported only as sum of the 3: HIV ENV pep pool. The ADAM should however contain also the 3 separated pools.

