In IPCAVD-003, 24 HIV-1 negative subjects were randomized 3:1 to receive a single vaccination with Ad26.ENVA.01 or placebo. Eight of the subjects were Ad26 seropositive at screening. The T-cell responses by IFNγ ELISPOT assays were slightly lower in the baseline Ad26-seropositive subjects; ICS and enzyme-linked immunosorbent assay responses proved comparable between subjects who were Ad26 seropositive and Ad26 seronegative at baseline, both in peripheral blood and in colorectal mucosa. In addition, systemic and mucosal responses persisted for at least 1 year in the majority of subjects after a single IM vaccine dose. These data suggest that the impact of baseline Ad26 nAbs, at the titers observed in that study, on the immunogenicity of this Ad26 vaccine is modest. Additionally, there were no consistent increases in Ad26-seronegative or Ad26-seropositive subjects.

A subset of volunteers in IPCAVD-001 and IPCAVD-004 was evaluated for shedding in urine and respiratory secretions after vaccination and during intercurrent illnesses; all shedding samples were negative for adenovirus.^{1,4}

gp120 Vaccines

A monovalent gp120 protein (AIDSVAX B) was tested in 671 healthy subjects at 3 doses, 100, 300, and 600 mcg. ¹⁷ The 300-mcg dose was found to be the most effective, inducing a higher Ab response without significant side effects. In the Thai trial RV144²⁶, the only vaccine study to date to demonstrate efficacy in prevention of acquisition of HIV, a bivalent gp120 protein (AIDSVAX B/E; 300-mcg dose) was used as a booster following priming with a recombinant canarypox vector (ALVAC-HIV) and afforded more than 30% protection from infection in the absence of either CD8⁺ T-cells or nAb to primary HIV isolates. Therefore, a similar dose (250 mcg) of Clade C gp140 was chosen for evaluation in this study.

For subjects who will receive a combination of Clade C and Mosaic gp140, the total dose will be 250 mcg (125 mcg of each protein). The total dose of aluminum phosphate adjuvant and gp140

protein (Clade C gp140 mixed 1:1 with Mosaic gp140) will not exceed the maximum doses that were tested in previous GLP toxicity studies (TOX10872 and TOX10873), ie, 250 mcg total gp140 protein + 425 mcg aluminum phosphate adjuvant.

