## **2.4. Definition of Subgroups**

The following subgroups will be investigated for the most relevant immunogenicity assays (more details in section 6.3):

- Region (Africa, USA)
- Ad26 VNA at baseline (<LLOQ, >=LLOQ)
- Sex (Female, Male)

- Race (Caucasian, Black or African American, Asian, Othera)
- BMI [ $<18.5$ ;  $18.5-<25$ ;  $25-<30$ ;  $\geq 30$ ]

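### The Ad26 VNA responder rule ignores baseline, so unchanged pre-existing antibody, in placebo recipients too, is counted as a response

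*SAP*

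**What the plan says.** The Ad26 VNA row of the SAP 6.5 table reads "Ad26 VNA Janssen Vaccines and Prevention 17 NA NA IC90 >LLOQ". Nothing else in the SAP defines an Ad26 VNA responder. The column holding the rule is headed "Responder definition/Positivity (if baseline is not available".

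In the same column the Env ELISA rule has two parts: "1) if baseline <LLOQ or missing, R>LLOQ 2) if baseline >=LLOQ, R=3-fold increase from baseline". ADCP and ELISpot have the same structure, using LOD and a test-specific threshold in place of LLOQ.

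SAP 2.4 lists the subgroup "Ad26 VNA at baseline (<LLOQ, >=LLOQ", so a baseline value is expected. SAP 6.2 lists Ad26 VNA among the humoral assays. For each of those, at each time point, SAP 6.3 specifies "geometric mean of actual values, geometric mean increases and percentage of responders, all with corresponding 95% CIs will be provided by group".

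The exclusion criteria in Protocol 4.2 (main study) and 4.5 (late boost) do not mention Ad26 serostatus. Protocol 1.1.2.1 describes an earlier 24-subject study of an Ad26 vaccine and says: "Eight of the subjects were Ad26 seropositive at screening".

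**The concern.** A responder rate should describe what happened after vaccination. With no baseline term, the Ad26 VNA rate mixes vaccine-induced antibody with antibody already present from natural exposure. The protocol's own background section shows that such exposure is to be expected, yet this row lacks the protection that three other assays in the table have.

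At stake is the reading of the exploratory objective on immune responses against the vector. The placebo group would show a sizeable percentage of responders with no vaccine effect, and the percentage could not separate a seropositive vaccinee whose titre rose from one whose titre did not.

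**Working it through.** The documents give no figure for this rate, so there is none to reproduce.

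**1. The two rules applied to example titres (LLOQ 17).** The 3-fold increase is read as at least 3-fold.

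| Baseline | Later titre | Ad26 VNA rule as written | Env ELISA rule |
|---|---|---|---|
| below 17 | 60 | responder | responder |
| 100 | 100 | responder | non-responder |
| 100 | 250 | responder | non-responder |
| 100 | 300 | responder | responder |
| 100 | 12 | non-responder | non-responder |
| 17 | 17 | non-responder | non-responder |

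The rules part only where baseline is positive, the later titre is above LLOQ and the rise is less than 3-fold. The last row shows a small boundary effect: a baseline of exactly 17 falls in the seropositive subgroup of SAP 2.4 but is not above LLOQ.

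**2. Expected placebo responders.** Inputs: n = 25 planned in Group 3 (Protocol 3.1), and p, the share seropositive at baseline. The documents do not give p for this trial, so it is an assumption: 8/24 borrowed from the earlier study, with a range of 10% to 60%. If titres are stable, the rule as written gives n × p:

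- p = 10%: 25 × 0.10 = 2.5
- p = 8/24: 25 × 0.333 = 8.3
- p = 60%: 25 × 0.60 = 15

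Even at 10%, the chance of at least one such responder is 1 − 0.90^25 = 93%. If 22 placebo recipients were evaluable, 8/24 would give 22 × 0.333 = 7.3. Under the two-part rule the expected number is about 0 throughout.

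**3. Effect on the vaccine-placebo contrast.** Let q be the response rate in seronegative vaccinees and r the share of seropositive vaccinees with at least a 3-fold rise. Assume titres that start above LLOQ stay there.

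- As written: vaccine (1 − p)q + p, placebo p, contrast (1 − p)q.
- Two-part rule: vaccine (1 − p)q + pr, placebo 0, contrast (1 − p)q + pr.

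Inflation is p(1 − r) in vaccine and p in placebo. The contrast therefore falls by pr.

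Illustration with p = 8/24, q = 0.90 and r = 0.50 (q and r are assumed and have no source in the documents):

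- Vaccine, two-part rule: 0.667 × 0.90 + 0.333 × 0.50 = 76.7%.
- Vaccine, as written: 0.667 × 0.90 + 0.333 = 93.3%, which is 16.7 points higher.
- Placebo: 33.3% as written against 0%, which is 33.3 points higher.
- Contrast: 93.3 − 33.3 = 60.0 points instead of 76.7.

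With r = 0.50, the loss pr runs from 5 points at p = 10% to 30 points at p = 60%.

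**4. Late boost.** Everyone eligible comes from the long-term extension and has had four Ad26 doses (Protocol 4.4 and 4.5). SAP 6.1 carries the main-study rules forward, and SAP 2 fixes baseline before the first dose. Take a late-boost placebo recipient with a first-dose baseline below 17, a pre-boost titre of 60 and a later titre of 60. That person is a responder under the rule as written and under the two-part rule with the first-dose baseline. Only a pre-boost reference, which would require 3 × 60 = 180, classes the unchanged titre as no response.

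**The case against.** The strongest defence is that little depends on this percentage. Protocol 2.1 defines the vector-immunity endpoint as a titre and places it among the exploratory endpoints. In the late-boost objective, Ad26 antibody at the time of vaccination is related to the ELISA response, which needs no responder rule. SAP 6.3 leaves Ad26 VNA out of its comparisons between the two active groups. It also reports geometric mean increases and plots individual values, so a group-level rise would be visible. All of this stands and limits the impact.

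The heading also mentions positivity, so the entry may have been meant as a seropositivity cut-off. That reading does not rescue the row. The heading reserves positivity for cases without a baseline, and the two-part rules write out the missing-baseline case explicitly. If positivity was the intention, the SAP has no Ad26 VNA responder rule at all. SAP 6.5 leaves the final framework to the data presentation specification (DPS), which is not among the documents reviewed; until it says otherwise, the SAP text governs.

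The TZM-bl rows use the same unconditioned rule, so Ad26 VNA is not the only such row. Pre-existing positivity is less expected there because participants must be HIV-negative at entry.

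Two stronger inferences are tempting, and neither is supported. A reader might suppose that the inflation is equal in the vaccine and placebo groups and so cancels; step 3 shows that it is larger in placebo. A reader might also suppose that a seropositive person is counted at every visit. The documents give humoral sampling visits but not the visits at which Ad26 VNA is run, and the count applies only while the titre stays above LLOQ. Main-study placebo recipients do not continue into the extension, so for them the effect largely ends at Week 72.

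**Conclusion.** The point holds and should be corrected. As written, the Ad26 VNA responder rate counts unchanged pre-existing antibody in any group at any assayed visit where the titre remains above LLOQ. In placebo this means about 8 of 25 if seropositivity is 8/24, or about 2.5 to 15 over an assumed 10% to 60%. The vaccine-placebo contrast is understated by the product of baseline seropositivity and the share of seropositive vaccinees with a 3-fold rise.

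These sizes are illustrative. The 8/24 comes from a different, small study whose cut-off is not stated, and the response rates in the illustration are assumed. No primary or secondary conclusion is affected. It would also go too far to infer that the plan cannot show a vector response: the geometric mean increases can show one at group level, although the responder percentage does not.

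**What to change.** In the Ad26 VNA row of SAP 6.5, use the two-part Env ELISA rule: baseline below LLOQ or missing, responder if above LLOQ; baseline at or above LLOQ, responder if the titre rises at least 3-fold. Report the percentage above LLOQ separately under the label *seropositive*, including at baseline.

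The documents do not establish that 3-fold is the right criterion for this particular assay. It is proposed because the SAP already uses it for other assays. If the entry was meant as positivity, label the output *percent positive* and show it by baseline serostatus.

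For the late boost, state in SAP 6.1 or 6.5 that the reference for this rule is the pre-boost titre. Also correct the cross-reference in SAP 6.3, which sends the reader to 6.4 for responder definitions that are in 6.5.

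The cost is one table cell, a sentence or two, and a small programming change. Fold-increase handling is already in SAP 6.4, Protocol 9.1.10 already collects a pre-dose immunogenicity sample at the late boost, and baseline titres are already planned. The reported vector-response rates will be lower.
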